6.2.1. Baseline Patient Demographic Survey

6.2.2. Medication Persistence

6.2.2.1. Definition: Continue to take medicines over time independent of adherence to the PrEP medication regimen.

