6.2.5. Adherence

6.2.5.1. Definition: Taking PrEP in line with medical advice/using PrEP appropriately (critical for efficacy) .

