6.2.6. Adherence Assessment CAB-LA

6.2.6.1. Adherence to the dosing schedule will be assessed at month 3 (early adherence) and end of study by:

A) Estimating the number of individuals who missed one or more consecutive injections without taking daily oral bridging PrEP while not on CAB-LA injections and mean and median number of injections missed during a 6- and a 12-month period.

6.2.7. B) Estimating the number of individuals who received the injections seven or more days later than their scheduled injection visit and the mean and median duration of delayed injections. Adherence Assessment Oral PrEP

6.2.7.1. Adherence to the dosing schedule will be assessed at months 3 (early adherence) and 12 by:

A) Estimating the number of individuals who reported three or more days of oral PrEP missed and the mean and median number of days they missed.

B) Estimating the number of individuals who had a gap of >90 days between the end of the days of supply of a dispensing and the start date of the next fill.

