To assess the co-primary endpoint of persistence at 3 months and end of study, the proportion of participants reporting continued receipt of injections in the CAB-LA cohort and the proportion of patients reporting continued use of PrEP by mouth in the oral PrEP cohort on the persistence assessment will be compared using chi square tests or Fisher's exact tests. Self-reported persistence will be validated by the medication possession ratio (MPR). MPR is defined as the number of days of medication dispensed during the study period divided by the number of days that the person should have received therapy. The percent of CAB-LA participants with MPRs ≥ 1.0 will be compared to the percent of oral PrEP participants with MPRs ≥ 1.0 using chi square tests or Fisher's exact tests. To assess the co-primary endpoint of adherence, chi square tests or Fisher's

exact tests will be used to compare the percent of CAB-LA participants who reported missing one or more injections during the study period to the percent of oral PrEP participants who reported three or more missed days of oral PrEP. The percent of CAB-LA participants who received any injections seven or more days later than their scheduled injection or oral PrEP participants who had a gap of >90 days between the end of the days of supply of a dispensing and the start date of the next fill will be compared.

Sample Size

Assuming adherence proportions of .90 and .65 and sample sizes of 70 and 35 in the CAB-LA and oral PrEP arms respectively, the 95% confidence interval for the difference between the CAB-LA proportion and the oral PrEP proportion is .0771 to .4229.

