You are treated with less respect than other people are. 
  Never  Less than once a year  A few times a year  A few times a month  At least once a week  Almost every day 	15
People act as if they're better than you. 
  Never  Less than once a year  A few times a year  A few times a month  At least once a week  Almost every day 	16
What do you think is the main reason for these experiences? (Select 1) 
  Your gender  Your sexual orientation  Your race  Your religion  Some aspect of your physical appearance  Your education or income level  Other: [Write in] 	17

End Message: Thank you for completing this survey!

Persistence Assessment

Activity Title: Are You Still Taking PrEP?

Activity Description: In this short survey, we'll ask you some questions about your PrEP journey and any challenges you may have encountered.

Activity:

1. Are you still taking PrEP medicine by mouth?

- Yes, I am taking PrEP (branching logic to question 4)
- No, I stopped taking PrEP (branching logic to questions 2)

2. Over the past week, how many days did you miss taking PrEP?

- 0
- 1
- 2
- 3
- 4
- 5
- 6

7

3. If you stopped taking PrEP, which of the following best describes the reason(s) why? [Select up to 2]

- I no longer feel I needed to take PrEP (branching logic to question 3 if selected)
- It was too difficult to take PrEP with my schedule
- I did not want people to know I was taking it or I felt I was being judged by others for taking PrEP
- I did not like the side effects
- I take too many medications
- There were too many appointments as part of my PrEP care
- I tested positive for HIV
- Other: [Fill in the blank]

4. Which of the following best describes why you no longer feel you need to take PrEP?

- I am no longer having sex
- I am in a monogamous relationship
- I am no longer using injectable drugs
- My partners and I are all regularly using condoms and getting tested for HIV
- Other: [Fill in the blank]

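### As worded, CAB-LA adherence is largely nested in persistence, and stoppers can be scored differently in the two arms of the co-primary adherence test

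*Combined protocol and SAP*

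**What the plan says.** Section 7 names persistence and adherence as co-primary endpoints and tests each with a chi-square or Fisher's exact test.

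- **Definitions.** Section 6.2.2 defines persistence as "Continue to take medicines over time independent of adherence to the PrEP medication regimen"; 6.14.1.1 repeats the independence. Section 6.2.5 defines adherence as "Taking PrEP in line with medical advice/using PrEP appropriately".
- **CAB-LA adherence.** Section 7 uses "the percent of CAB-LA participants who reported missing one or more injections during the study period". Section 6.2.6.1 describes a similar event but exempts misses covered by oral bridging. It also asks for the "mean and median number of injections missed during a 6- and a 12-month period".
- **Oral adherence.** Sections 6.2.7.1 and 7 use three or more missed days. Section 6.2.7.1 gives assessment months (3 and 12), but neither section gives a look-back period. The only item on missed days is question 2 of the Appendix C Persistence Assessment: "Over the past week, how many days did you miss taking PrEP".
- **Second adherence comparison.** Section 7 also compares CAB-LA participants given an injection at least a week late with oral participants who had a gap of more than 90 days before their next fill.
- **Stopping.** Section 6.6.1 treats more than three consecutive missed months as discontinuation. Section 6.5.1 removes participants who switch regimen before six months. No section says how a participant who stops enters either adherence count.
- **Sample Size.** "Assuming adherence proportions of .90 and .65 and sample sizes of 70 and 35 in the CAB-LA and oral PrEP arms", "the 95% confidence interval for the difference between the CAB-LA proportion and the oral PrEP proportion is .0771 to .4229".

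**The concern.** If injections due after a participant has stopped count as missed, one act of stopping fails two co-primary endpoints that the plan presents as distinct. The adherence result would then partly repeat the persistence result.

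The oral arm has no matching rule. Whether an oral stopper is scored as non-adherent, or is not scored at all, depends on who reaches a one-week recall item. The arm difference in adherence could then reflect how stoppers are handled rather than how people take PrEP while on it, and the choice could be made after the data are seen.

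**Working it through.** **Step 1: reproduce the stated interval.** Inputs from Sample Size: .90 of 70 and .65 of 35.

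SE = √(.90×.10/70 + .65×.35/35) = .0882. Interval: .25 ± 1.96×.0882 = .0771 to .4229, as printed. The plan states no power. A two-sided 5% test (pooled variance under the null, unpooled under the alternative) has about 85%.

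**Step 2: is CAB-LA adherence nested in persistence?** Injections fall at months 0, 1, 3, 5, 7, 9 and 11 (6.13.1), so gaps are one or two months. Discontinuation needs more than three missed months (6.6.1), which always spans a due injection within the schedule. A participant who reports at month 11 having stopped, and who did not receive that injection, has missed at least one. On the plain reading of Section 7 that participant is non-adherent. The reverse does not hold: a participant can miss one injection, resume, and still be persistent. The endpoints are nested, not identical.

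**Step 3: who supplies the oral data?** In Appendix C, question 1 sends those still taking PrEP to question 4 and those who stopped to question 2, the missed-days item. As printed, current users skip the item. Moving both targets down by one would not repair this, since then nobody would reach question 2. The CAB-LA form (Appendix B) has no item on missed injections.

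**Step 4: size.** The documents give no stopping rates, so every rate below is an assumption. Where stoppers count as non-adherent, measured adherence = (1 − stopping rate) × on-treatment adherence. Intervals use the Step 1 formula.

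*(a) .90 and .65 read as on-treatment values; stoppers counted only in CAB-LA.*

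| CAB-LA stopping | CAB-LA | Difference from .65 | 95% CI | Power |
|---|---|---|---|---|
| 0% | .90 | .25 | .0771 to .4229 | 85% |
| 10% | .81 | .16 | −.0228 to .3428 | 44% |
| 20% | .72 | .07 | −.1198 to .2598 | 11% |

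*(b) On-treatment adherence .90 in both arms; stopping 10% CAB-LA and 35% oral; stoppers counted in both.* CAB-LA .90×.90 = .81; oral .65×.90 = .585; difference .225 (CI .0377 to .4123). Dosing behaviour on treatment is identical, so the whole difference is persistence.

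*(c) On-treatment adherence .90 and stopping 20% in both arms.* Stoppers counted only in CAB-LA: .72 − .90 = −.18 (CI −.3247 to −.0353). Counted only in oral: .90 − .72 = +.18 (CI .0155 to .3445). The sign follows the handling of stoppers.

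**Step 5: the second comparison.** A permanent CAB-LA stopper receives no late injection, and a permanent oral stopper has no next fill. Stopping for good triggers neither event, so this comparison does not have the overlap.

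**Step 6: precision if adherence is limited to those still on the regimen.** At assumed stopping of 10% and 35%, n = 63 and 23 (35×.65 = 22.75, rounded). SE = √(.09/63 + .2275/23) = .1064; interval .25 ± .2085 = .0415 to .4585, power about 75%. At 20% and 50%, n = 56 and 18, the interval is .0161 to .4839 and power about 68%.

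**The case against.** A reader might infer that every CAB-LA stopper is non-adherent and that CAB-LA adherence can never exceed persistence. The documents do not support that. The event is reported misses, the CAB-LA form has no item for them, and there is no missing-data rule. A stopper who no longer answers could be missing, or could count as adherent. Someone who stops after the month-11 injection has missed none. That later injections count as missed is the plain reading, but no text states it, and scoring a medically advised stop as non-adherence sits badly with the definition in 6.2.5.

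A reader might also infer that the rule works against CAB-LA. That needs current oral users to answer the missed-days item and oral stoppers to drop out, the opposite of the printed routing. The direction is not fixed.

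Nor can it be said that the plan has no adherence measure free of the overlap: the late-injection and refill-gap comparison is one for permanent stoppers. Section 6.2.6.1 also exempts bridged misses, which Section 7 does not mention.

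Finally, nested endpoints are not an error in themselves. A composite that fails stoppers is a legitimate choice, and both protocol summaries name persistence alone in the primary objective. These points narrow the concern. What stands is that the first adherence test, as written, has no common rule for stoppers, uses different periods and sources by arm, and is called co-primary.

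**Conclusion.** The concern holds in limited form. On the plain reading of Section 7, with the schedule and discontinuation rule, CAB-LA adherence is largely nested in persistence despite definitions that separate them. Stoppers can be scored differently by arm in a co-primary test.

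The size depends on assumed stopping rates and on how stoppers are handled. In the examples the planned .25 shrinks to .16 or .07, or a difference of .225 appears with no difference in on-treatment adherence. Neither the direction nor the size can be settled from the documents. Sample Size does not say whether .90 and .65 include stoppers. If .90 does, on the plain reading at most 7 of 70 CAB-LA participants can stop before month 11 (70 − .90×70 = 7).

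**What to change.** 1. **One rule, one period.** In 6.2.6, 6.2.7 and Section 7, count injections or days due from initiation to a discontinuation date derived from injection and dispensing records, the same way in both arms. For permanent stoppers, set the date at the first injection due and never given, or at the end of the last dispensed supply, so that stopping is not itself a counted miss. Dating it from when the 6.6.1 criterion is met would leave the overlap in place. This is a derived analysis date and changes nothing in clinical management.
2. **Composite alongside.** Report with equal prominence a composite over all initiators (persistent and adherent at end of study), with stoppers as failures in both arms. The on-treatment measure has unequal exposure and can favour early stoppers, so it should not stand alone.
3. **Data sources.** Take missed injections from injection records. Correct the oral form so that current users answer the missed-days item, and state the look-back for the oral event.
4. **Bridging.** Reconcile 6.2.6.1 and Section 7 on whether a miss covered by oral bridging counts.
5. **Sample Size.** State which measure .90 and .65 describe. If it is limited to those still on the regimen, give the wider interval (.0415 to .4585 in the first example of Step 6).

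The cost is SAP wording, one derived date per participant and a correction to one form. If the oral form has already been used as printed, missed-days answers from current users may not exist and cannot be recovered.

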You are treated with less respect than other people are. 
  Never  Less than once a year  A few times a year  A few times a month  At least once a week  Almost every day 	15
People act as if they're better than you. 
  Never  Less than once a year  A few times a year  A few times a month  At least once a week  Almost every day 	16
What do you think is the main reason for these experiences? (Select 1) 
  Your gender  Your sexual orientation  Your race  Your religion  Some aspect of your physical appearance  Your education or income level  Other: [Write in] 	17

End Message: Thank you for completing this survey!

Persistence Assessment

Activity Title: Are You Still Taking PrEP?

Activity Description: In this short survey, we'll ask you some questions about your PrEP journey and any challenges you may have encountered.

Activity:

1. Are you still getting PrEP medicine by an injection from your healthcare provider?

- Yes, I am taking PrEP ([branching logic to question 4](#))
- No, I stopped taking PrEP ([branching logic to question 2](#))

2. If you stopped taking PrEP, which of the following best describes the reason(s) why?

[Select up to 2]

- I no longer feel I needed to take PrEP ([branching logic to question 3 if selected](#))
- It was too difficult to take to take PrEP as prescribed with my lifestyle
- I felt I was being judged by others for taking PrEP
- I experienced side effects from taking PrEP

- I take too many medications
- There were too many appointments as part of my PrEP care
- I tested positive for HIV
- Other: [Fill in the blank]

3. Which of the following best describes why you no longer feel you need to take PrEP?

- I am no longer having sex
- I am in a monogamous relationship
- I am no longer using injectable drugs
- My partners and I are all regularly using condoms and getting tested for HIV
- Other: [Fill in the blank]

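### The co-primary adherence test sets any missed injection over the whole study against an oral missed-day event that has no stated window or rule for combining reports

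*Combined protocol and SAP*

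**What the plan says.** Section 7 (Statistical Analyses) names adherence as a co-primary endpoint and tests it by chi-square or Fisher's exact test. The contrast, with the CAB-LA side first, is worded: "reported missing one or more injections during the study period to the percent of oral PrEP participants who reported three or more missed days". The CAB-LA side has a period attached; the oral side has none.

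Section 6.2.7.1 repeats the oral threshold: "Estimating the number of individuals who reported three or more days of oral PrEP missed and the mean and median number of days they missed". It opens with "Adherence to the dosing schedule will be assessed at months 3 (early adherence) and 12 by", which fixes when adherence is assessed. It does not say how far back a report looks or how two reports combine.

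The only instrument item that counts missed pills is question 2 of the oral Persistence Assessment in Appendix C: "Over the past week, how many days did you miss taking PrEP". Section 6.2 schedules that assessment monthly, 12 times in all.

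The CAB-LA Persistence Assessment in Appendix B asks "Are you still getting PrEP medicine by an injection from your healthcare provider", then reasons for stopping, challenges, and whether a provider asked about difficulties. No item asks about a missed injection.

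Section 6.2.6.1 counts a CAB-LA participant only if injections were missed without oral bridging. Section 7 does not mention bridging.

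**The concern.** A between-arm test needs the event to mean the same thing in both arms, or at least to be observed over the same time. Here a CAB-LA participant has six follow-up injections (Section 6.13.1: months 1, 3, 5, 7, 9 and 11), and missing any one of them makes the participant non-adherent. An oral participant can be caught only in the weeks that a survey covers. How many of those weeks count, and whether one bad week is enough, is left open.

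Two analysts following Section 7 could thus produce different oral proportions from the same answers and reach opposite conclusions on a co-primary endpoint. The CAB-LA proportion also depends on whether bridged injections count. The only precision statement in the plan concerns adherence, and its oral value of .65 is tied to no definition.

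**Working it through.** **1. The plan's own figure.** Section 7 assumes adherence of .90 (n = 70) and .65 (n = 35). The unpooled standard error is sqrt(0.90×0.10/70 + 0.65×0.35/35) = 0.08824. The interval is 0.25 ± 1.96×0.08824 = 0.0771 to 0.4229, as stated. The arithmetic is right; the question is what .65 measures.

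**2. What .65 would imply.** Non-adherence of 0.35 on one past-week report needs a daily miss rate of about 30%, since P(X ≥ 3 | 7, 0.30) = 0.353. If it means any of 12 reports, the chance per report is only 1 − 0.65^(1/12) = 0.035.

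**3. Days observed in the oral arm.**
- One report: 7/365 = 1.9% of the year.
- Months 3 and 12: 14/365 = 3.8%.
- All 12 reports: 84/365 = 23%.

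The CAB-LA event covers the full study period.

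**4. Oral non-adherence by reading.** Assumption, not in the documents: every oral user misses 10% of days, independently.
- One survey: P(X ≥ 3 | 7, 0.10) = 0.0257.
- Month 3 or 12: 1 − (1 − 0.0257)^2 = 0.051.
- Any of 12: 1 − (1 − 0.0257)^12 = 0.268.

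The any-of-12 figure moves strongly with the assumed daily rate: 4.4% at a 5% rate and 85% at a 20% rate. The one-survey figure goes from 0.4% to 15% over the same range.

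**5. CAB-LA non-adherence.** The plan's .90 gives 10%, which corresponds to a miss chance per injection of 1 − 0.90^(1/6) = 1.7%. As an upper illustration, an assumed 5% per injection gives 1 − 0.95^6 = 26.5%.

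**6. Rejection rates.** These use exact enumeration of the two binomials at n = 70 and 35 with a pooled z-test (equivalent to the uncorrected chi-square). Two-sided 5% is assumed, because Section 7 gives no alpha for this test.

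| Oral reading | Oral non-adherence | CAB-LA 10% (plan) | CAB-LA 26.5% (assumed) |
|---|---|---|---|
| One survey | 2.6% | about 18%, favouring oral | about 94%, favouring oral |
| Month 3 or 12 | 5.1% | about 8%, almost all favouring oral | about 82%, favouring oral |
| Any of 12 | 26.8% | about 61%, favouring CAB-LA | about 5%, both directions |

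Fisher's exact test gives lower rates in the same pattern: 17%, 7% and 54% in the plan's column, and 93%, 80% and about 4% in the other.

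**The case against.** Four points on the other side deserve weight.

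*Section 6.2.7.1 narrows the choice.* It fixes months 3 and 12, so the natural readings are one report per time point or either of two. No passage proposes any of 12, or a sum of missed days over the 84 surveyed days (which would give 99.2% in this illustration). A reader might therefore infer an uncertainty running from 2.6% to 99.2%; the documents do not support that full range. What stands is that Section 7 does not carry the time points over and the item is asked monthly, so any of 12 is not excluded. Even the narrow reading observes at most 14 days against the full study period.

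*The plan never says past week in the test.* A reader might infer that the plan sets an 11-month event against a 7-day snapshot. That is one reading. The 7-day recall comes only from the Appendix C item; Section 7 leaves the oral window blank.

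*Missed injections can be counted.* A reader might infer that the CAB-LA numerator cannot be obtained. The Study Outcomes Table lists the EHR alongside the survey as a source for the primary endpoint, and injections are given at scheduled clinic visits. The defect is that the test is worded on self-report with no item behind it.

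*Different products need different cut-offs.* A daily pill and an injection about every two months share no unit of missed dose. That supports describing each arm in its own terms. It does not support a chi-square test between events seen over unequal periods.

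The skip in Appendix C that sends oral participants still on PrEP past question 2 is a separate error. Correcting it leaves the windows unmatched.

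**Conclusion.** The point stands. Followed as written, Section 7 gives a co-primary test on unequal windows, with the oral window and combining rule unstated, no self-report item behind the CAB-LA numerator, and bridging treated differently from Section 6.2.6.1.

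Under the plan's 10% CAB-LA non-adherence and an assumed 10% independent daily miss rate, the same behaviour leads to rejection in about 18% of studies favouring oral, or about 61% favouring CAB-LA, depending only on the reading. The 94% figure should not be the headline. It needs a 5% miss chance per injection, which conflicts with the plan's .90.

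The sizes rest on independence and on one common miss rate for all users, neither of which the documents give. Other values change the sizes. The dependence on the reading comes from the missing definition.

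**What to change.** In Section 7, base the between-arm adherence test on one measure with the same window and the same cut-off in both arms. An example is the proportion of days covered from clinic injection dates and WVHR pharmacy fill dates, month 0 to month 11. Before analysis, state the cut-off and how oral bridging is counted, and reconcile Sections 6.2.6.1, 6.2.7.1 and 7.

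Take missed injections from the clinic record. Report the missed-injection count and the past-week missed-day item as within-arm descriptions, naming the surveys used and how they are combined, and do not test one against the other.

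If the sponsor keeps the present comparison, the least it must do is state the window, data source and combining rule in each arm. That removes the ambiguity but not the inequality of the windows.

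The cost is SAP wording. Dispensing data are already needed for the medication possession ratio (MPR), and injection dates for the late-injection comparison. There are two downsides. Fills do not prove that pills were taken, and the measure overlaps with the MPR comparison already in Section 7. Self-report therefore stays as supportive information.
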